# F. Study Procedures

#### F1. Screening Procedures

This study will be conducted in accordance with current US FDA regulations and guidelines, ICH guidelines on GCP, the principles of the Declaration of Helsinki, as well as all other applicable national and local laws and regulations. Patients will be screened by fully qualified research coordinators at each clinical center based upon the inclusion and exclusion criteria. Verification of active pulmonary sarcoidosis will include review of pathology reports and/or tissue samples (if available), and review of radiographs (chest x-ray and/or lung CT scans) by a board-certified pulmonologists (i.e., the site PIs). A chest x-ray will be performed if the patient has not had one done within the past year. A thorough history and physical exam will be conducted and an ECG will be routinely obtained (if not already available) to screen for cardiac disease and other exclusion criteria, as described above.

#### F2. Schedule of Measurements

The schedule for study visits including the assessments and procedures to be performed at each visit is presented in the Schedule of Events (see Table 1). The scheduled study visits should occur at the specified week post-randomization  $\pm$  7 days unless otherwise specified. It is encouraged that study visits be scheduled in the morning, at the same time for each visit, unless extenuating circumstances exist. In addition to scheduled visits, monthly telephone interviews will be conducted by the study site research coordinators to establish/encourage compliance with nicotine (placebo) patches and to screen for adverse events.

#### F3. Safety and Adverse Events

Safety analyses will be based on treatment received. Safety data, including but not limited to, AEs, serious AEs (SAEs), infections, serious infections, mortality, changes in laboratory assessments, and changes in vital signs. Treatment-emergent AEs will be summarized by treatment group.

All untoward events occurring between the time of obtaining informed consent through Week 34 must be reported as an AE. In keeping with the standards of clinical trials research, the relationship of AEs to nicotine will be classified as "definitely related", "possibly related" or "unrelated", and we will further document the reason for subject dropout, report subjects with multiple adverse events, and track disease exacerbations (requiring escalation of corticosteroid dose or unscheduled healthcare visits).

The severity of AEs will be made using the following general categorical descriptors:

- **Mild:** Awareness of symptoms that are easily tolerated causing minimal discomfort and not interfering with everyday activities.
- Moderate: Sufficient discomfort is present to cause interference with normal activity.
- **Severe**: Extreme distress causing significant impairment of functioning or incapacitation and preventing normal everyday activities.

Based upon our pilot study (11) and previous published reports (33), we expect to see an increase in the frequency of mild side effects with no significant SAEs in the nicotine treatment group compared to placebo controls. These minor side effects tend to abate with continued use of nicotine, and only one subject withdrew from the pilot study due to local skin irritation at the site of the patch. For this reason, we will encourage the subjects to alter the site of the transdermal patch on a daily basis.

There is a potential for a placebo effect with respect to the use of a patch in the nicotine treatment group compared to controls. However, a placebo effect would be expected to influence subjective measures (e.g., dyspnea scores); whereas, objectives measures of lung function or radiographic findings would be effected very little, if at all.

Subjects will be instructed to call the investigator if their symptoms of sarcoidosis worsen. Based upon the investigator's assessment of the subject's symptoms, functional parameters, and the subjects' history, a clinic visit may be scheduled. If in the investigator's opinion the symptoms of sarcoidosis have worsened sufficiently to require treatment, the investigator will assess the severity and initiate appropriate treatment depending upon the subject's condition. Despite escalation of treatment, the patient will remain enrolled in the study.

Patients will be followed for an additional 4 weeks after nicotine treatment to determine if they required any change in medications, including escalation of therapy for sarcoidosis, and to screen for signs of nicotine dependency or withdrawal. Although nicotine dependency did not occur in the pilot study and is documented to be rare in the setting of transdermal preparations (33), likely due to steady and sustained drug levels (45,46), it remains a potential concern. As such, study subjects demonstrating nicotine dependency or addiction symptoms (e.g., nicotine craving or inability to discontinue nicotine-containing products) one month after discontinuation of the drug will be provided support to engage in a smoking cessation program, which has extensive experienced with nicotine dependency and addiction management (51).

#### F4. Study Outcome Measurements and Ascertainment

The primary endpoint of the study will be the change in FVC, measured before and after treatment with nicotine or placebo for a total of 24 weeks.

The secondary clinical endpoint of major interest will be the change in total burden of lung disease, as reflected by the computer-generated CT image analysis or changes in lung function. Data files will be deidentified and thereby blinded to the investigative team. Moreover, the computer-generated Lung Texture Score (LTS) ascertained from these analyses are objective, highly reproducible, and strongly correlate with standard physiological (PFT) measures (32).

Other secondary endpoints will determine if changes in LTS correlate with changes in simultaneous PFT measures or measures of the rate of nicotine metabolism, as reflected by the ratio of 3-hydroxycotinine to cotinine in serum samples. Finally, the effects of nicotine treatment on disease-related symptoms will be determined by comparing the results of surveys (SAT, SGRQ, FAS) conducted at regular intervals during the study protocol. Again, these analyses will remain blinded to treatment allocation until the close and un-blinding of the study.

#### PFT measurements:

The post-bronchodilator FVC, forced expiratory volume in 1 second (FEV1), peak expiratory flow rate (PEFR), and forced expiratory flow at 25% to 75% of vital capacity (FEF25-75) will be measured according to the body temperature, pressure, and saturation (BTPS) standard convention. PFTs will be repeated up to 8 times to obtain 3 acceptable readings according to American Thoracic Society (ATS) guidelines. Acceptable repeatability is achieved when the difference between the largest and the next largest FVC is  $\leq 0.150$  L and the difference between the largest and the next largest FVC is to 0.150 L and the difference between the largest FEV1 is  $\leq 0.150$  L. However, if a subject is too tired to meet this consistency requirement, the PFT values from the best effort can still be accepted as long as this best effort meets the other ATS criteria. Subjects should refrain from using short acting bronchodilators for at least 4

hours and long-acting bronchodilators for at least 12 hours prior to the screening visit. Percent predicted FVC and FEV1 will be calculated according to the Crapo equation (52), with correction for race.

CT scans and x-ray: CT scans will be performed at the baseline assessment or within 3 months prior to enrollment so long as the following criteria are also met: 1) the CT scan was obtained for clinical reasons and on the same scanner used for the research study, 2) the patient's sarcoidosis treatment regimen was unchanged within the past 3 months, and 3) respiratory symptoms (cough, dyspnea) were stable. The imaging protocol will be standardized across the clinical centers: Non-contrast CT scans will be obtained by using a helical technique with a 16- or 64-detector row CT scanner. Images will be obtained from lung apices to the lung bases in a single breath hold with the following parameters: collimation, 1.25 or 0.625 mm; field of view, 36 cm; beam pitch, 1.35 or 1.375; gantry speed, 0.5 or 0.6 sec/rotation; 120 kVp; 150-200 mA. The image files will be sent from a proxy PACS server located at each clinical center and transferred via a Virtual Private Network (to assure data confidentiality) and processed by [name] via a workstation located within the Department of Radiology at OSU. The image data will be reformatted with a 5-mm section thickness using standard lung algorithms. The lung image files are then segmented using Houndsfield units (-200 to -1000). and a two-point correlation function based approach to determine the presence of texture mismatches representing diseased lung is conducted within each volume of lung tissue using a proprietary plug-in program that can be operated on the publicly available NIH Image J Toolkit (http://rsbweb.nih.gov/ij/index.html) to create a regional lung texture score (LTS). The LTS for a given volume is integrated into an LTS for the entire lung, reflecting the overall burden of lung disease (32).

A chest x-ray will be performed at screening if one has not been done within the past year.

Prior to all radiation procedures, a urine pregnancy test will be done. If the result of the urine pregnancy test is positive, a serum pregnancy test will be done. P

**Blood draws**: Study subjects will undergo scheduled venopuncture under sterile technique for the purpose of obtaining 10 ml of blood to measure nicotine and nicotine metabolites (at baseline, 10 and 28 weeks). The blood samples will be labelled with the same identifier used for the subject's web-based data entry (REDCap), and will be stored on site at OSU and CCF at -80° F in a secure (password protected) laboratory until the final analysis for nicotine and related metabolites (cotinine). The samples from CCF will be shipped by same-day delivery on dry ice (i.e., -80 ° F) as a single batched sample prior to analysis.

*Surveys*: Well-standardized surveys will be administered according to the Study Schedule of Events (Table 1). These will be conducted during scheduled study-related visits or by mail (self-addressed first class mail through the US postal service). The following standardized surveys will be employed (examples of each are provided in the Appendix):

The **Fatigue Assessment Scale** (FAS) is a 10-item patient self-report instrument with five items reflecting physical fatigue and five assessing mental fatigue. The response options range from never (1) to always (5) for a total score from 10 to 50. Psychometric qualities are reported as satisfactory by the authors, and the instrument has been able to differentiate healthy respondents from patients with sarcoidosis (53,54).

The **St George's Respiratory Questionnaire** (SGRQ) is a disease-specific survey instrument designed for use with adult subjects to assess the impact of respiratory disease and its treatment on the subject's health outcomes (55). The SGRQ is self-administered and is usually completed within 10 to 20 minutes. The instrument contains 76 items in three domains: symptoms (frequency and severity), activity limitations, and impacts on social and psychological functioning. The response categories use a Likert scale or dichotomous

responses. The methods used for development of the instrument have not been published and criteria for item selection are unclear. The psychometric properties have been reported to be adequate. The instrument has been used extensively in research with asthma, chronic obstructive pulmonary disease (COPD), cystic fibrosis, IPF, and interstitial lung disease.

The **Sarcoidosis Assessment Tool** (SAT) is a self-administered health-related quality-of-life (HRQL) instrument that is validated against other standardized HRQL instruments for patients with active sarcoidosis and is further validated to specifically detect changes in the severity of lung involvement (56).

## G. Statistical Plan

#### G1. Sample Size Determination and Power

Depending on the clinical efficacy of nicotine compared to another immune modulating agent (infliximab), we expect to see up to 3% improvement in FVC in the nicotine treatment group based upon a comparable study design in patients with active pulmonary sarcoidosis (27). With the expected 25 patients per group and average change variance at a minimum of 3% for FVC, the precision of a comparison of means is roughly adequate for planning, but is insufficient for achieving significance unless the nicotine effect on FVC is large (e.g., >5%) as compared to controls. We will report *p*-values for these as secondary outcomes, and derive meaning only if our primary outcome (FVC) shows significance, i.e. we will use some of the logic of gatekeeping hypothesis testing (57). Assuming 5-10% variance (standard deviation) between consecutive FVC measurements, and a 3% change in FVC with treatment the estimated study size would range from 44-178 in each arm of the subsequent Phase II trial.

Our pilot study was not designed to detect radiographic changes after nicotine treatment (11). However, based upon the results of a recent Phase II sarcoidosis clinical trial structured almost identically to the study proposed herein (total **n = 40/group**), wherein the radiologist-generated "radiology score" (R-score) change from baseline was >30% post-treatment with low dose (3 mg/kg) anti-TNFα drug (i.e., 3.11 to 2.07, on a scale from 0-4 with "4" being most severe disease, p < 0.001) and changed significantly relative to matching controls [i.e., net change -1.33 (+0.29  $\pm$  2.21 for controls and -1.04  $\pm$  2.02 for treatment group, p < 0.001)] (27), we predict that 55 patients in each group (nicotine treatment and control) will be sufficient to detect a 15% difference in LTS score change before and after treatment with 90% power and type I error at 0.05 assuming a standard deviation of LTS score change at 20%. We consider the latter to be a conservative assumption based upon previous texture-based computerized volumetric CT analysis studies (as will be employed for this study) designed to detect changes in lung nodules of varying sizes over time wherein the standard deviation in the volumetric score was less than 10% across a broad range of nodule sizes and textures, including solid and ground glass densities (which are very common in sarcoidosis patients) (57). Of note, if the standard deviation of the LTS is closer to 10%, this study size will be sufficient to detect a 5-10% change in LTS with a power of ~42-94%. Thus, this pilot study may underpowered to detect a significant change in the LTS following nicotine treatment, but will be useful for estimating the study size required for a subsequent adequately powered Phase II trial.

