# E. Study Design

#### E1. Overview of Design Summary

This will be a prospective, randomized, parallel design with multiple measures, double-blinded, placebocontrolled study conducted on adults with confirmed sarcoidosis (e.g., biopsy proven, or a clinical diagnosis made by sarcoidosis experts) sarcoidosis to determine the effects of transdermal nicotine treatment in patients with active pulmonary disease despite conventional therapies. Patients will be enrolled sequentially and based solely on eligibility. Patients will be randomized in a 1:1 ratio to receive transdermal nicotine 21 mg/daily or an identical-appearing placebo patch. Baseline measurements will be made at the screening and baseline visits on all patients prior to receiving their randomized assigned treatment to a nicotine treatment group (n = 25 patients) and a control group (n = 25 patients) assigned to placebo patch treatment. Nicotine treatment will begin with a 2 week phase in during which the dose of nicotine will be increased weekly towards the highest tolerated dose, using the transdermal drug delivery approach (7 mg patch, 14 mg patch, 21 mg patch). Patients will be maintained on the highest tolerated dose (7-21 mg patch) for the duration of the 24 week treatment protocol. Nicotine treatment will then be deescalated weekly (i.e., 14 mg, 7 mg, and then discontinued).

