#### G2. Interim Monitoring and Early Stopping

As above, we conservatively predict that nicotine treatment will result in a 3% and 10% reduction in FVC and LTS, respectively, relative to the control group. In the spirit of a pilot study, we are unsure of the potency of nicotine in terms of preventing progression or promoting regression of disease, as reflected by the LTS.

Moreover, there is a possibility that nicotine treatment could be ineffective or associated with serious sideeffects in too many patients. As such, the DSMC will continuously monitor the progress of the study and will consider early discontinuation of the trial if nicotine treatment is associated with excess serious adverse events (SAE) (arrhythmias, seizures, syncope, new cancers, death).

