#### G4. Statistical Methods

The primary study endpoint will determine if nicotine treatment improves an objective measure of lung function that is commonly used in sarcoidosis clinical trials, and is considered to be the "gold standard" clinical endpoint for assessing clinical response in the setting of pulmonary disease activity (59). We will use a longitudinal model, which has certain advantages over the usual ANCOVA (using baseline LTS as covariate) (60). In this analysis both baseline and and post intervention LTS are dependent variables in the longitudinal model (60). Using SAS's Proc Mixed (61), all patients will be included in analysis, whether they are missing either a baseline (unlikely to happen) or a post intervention measurement. Included in the fixed effects model will be race and gender. Interactions with either will only be explored in a sensitivity analysis. With just two measures, we will use a saturated covariance structure (which allows the variances of the baseline and post measures to differ).

For the LTS scores, a longitudinal model, as described in Aim 1, will be used to compare LTS results in each treatment group at baseline and at the completion of the 24 week treatment protocol. Correlation between FVC and LTS: Bivariate plots will be used to describe the relationship between changes in FVC (Aim 1) and LTS (Aim 2). With 25 patients in the nicotine group, where substantial correlation of changes is expected, the standard error of the correlations will be ~0.15 for moderate values.

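### G1 claims 90% power for LTS at 55 per group, but the trial enrols 25 and the stated inputs need 38-39; at SD 20%, power at 25 is about 74% for a 15% difference and 41% for 10%

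*Combined protocol and SAP*

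**What the plan says.** Section G1 sizes the LTS comparison as follows: "we predict that 55 patients in each group (nicotine treatment and control) will be sufficient to detect a 15% difference in LTS score change", "with 90% power and type I error at 0.05 assuming a standard deviation of LTS score change at 20" per cent. The plan calls that SD conservative. Two sentences later it considers an SD nearer 10% and says "this study size will be sufficient to detect a 5-10% change in LTS with a power of ~42-94" per cent. The paragraph closes by conceding that "this pilot study may underpowered to detect a significant change in the LTS following nicotine treatment".

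Elsewhere the trial is smaller. E1 describes a "nicotine treatment group (n = 25 patients) and a control group (n = 25 patients"). The FVC paragraph of G1 starts "With the expected 25 patients per group". G4 says "With 25 patients in the nicotine group, where substantial correlation of changes is expected". G5 assumes 10% dropout and expects about 22 per arm with complete data.

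On the expected effect, G2 says "As above, we conservatively predict that nicotine treatment will result in a 3% and 10% reduction in FVC and LTS", relative to control.

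**The concern.** The only power the plan gives at its conservative SD belongs to a sample size the trial does not have. The size is also not what the stated inputs produce. Nothing in the sentence assigns 55 to a later study, whereas the FVC paragraph of G1 does assign its own range of 44-178 per arm to the next trial. A reader will therefore take 55 and 90% as describing the present design.

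LTS is the subject of Aim 2, and F4 names it as the main secondary endpoint. If the LTS comparison is null, the reader needs to know how likely the trial was to detect the effect it planned for. The paragraph offers 90% power at one point and a warning of low power at another, with no figure at SD 20% for 25 per group to connect them.

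**Working it through.** **Inputs.** From G1: difference 15%, SD of change 20% (alternative 10%), power 90%, alpha 0.05. From E1, G1 and G4: 25 per group. From G5: 10% dropout, about 22 completers per group. From G2: predicted difference 10%. The plan does not state sidedness, so two-sided is assumed.

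**Formulas** (normal approximation, equal groups; Δ is the difference, n is per group):
- size: n = 2(z₀.₉₇₅ + z₀.₉₀)² (SD/Δ)²
- power: Φ( (Δ/SD)·√(n/2) − 1.960 )

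The two-sample t-test (noncentral t) is given alongside.

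**Step 1: the plan's 55.** n = 2 × (1.960 + 1.282)² × (20/15)² = 2 × 10.51 × 1.778 = 37.4, so 38 per group. The t-test gives 38.3, so 39. With 10% dropout, 38/0.9 = 42.2 and 39/0.9 = 43.3, so 43-44 randomised. The 55 is not reproduced. A one-sided test gives 31-32. Only assumptions the plan does not state come close:
- 30% dropout: 38/0.7 = 54.3, so 55
- alpha 0.01: 53
- a 12.5% difference: 54
- an SD of about 24%: 55
- reading 20% as the SD of a single measurement, with baseline-to-follow-up correlation of 0.25-0.30: 57-53

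**Step 2: power at 55 for the stated inputs.** 0.75 × √27.5 = 3.933, and Φ(3.933 − 1.960) = 97.6% (t-test 97.4%).

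**Step 3: the range of about 42-94% at SD 10%.**
- At 25 per group, 5%: 0.5 × √12.5 = 1.768, Φ(−0.192) = 42.4%.
- At 25 per group, 10%: 1.0 × √12.5 = 3.536, Φ(1.576) = 94.2%.
- At 55 per group: 74.6% and 99.95%.

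Among the sizes the plan names for this trial (22, 25 and 55), the range fits 25 only. By t-test, 26 per group would give the same two figures, but the plan nowhere mentions 26.

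**Step 4: power of the actual design** (t-test on change scores, normal approximation in brackets).

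| SD | Difference | 25 per group | 22 per group | 55 per group |
|---|---|---|---|---|
| 20% | 15% | 73.8% (75.5%) | 68.1% (70.1%) | 97.4% (97.6%) |
| 20% | 10% | 41.0% (42.4%) | 36.7% (38.1%) | about 74% (74.6%) |
| 10% | 5% | 41.0% (42.4%) | 36.7% (38.1%) | about 74% (74.6%) |
| 10% | 10% | 93.4% (94.2%) | 90.0% (91.3%) | 99.9% (99.95%) |

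At SD 20%, 90% power (t-test) is reached only for a difference of 18.7% with 25 per group, or 20.0% with 22.

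**Step 5: size for the 10% difference in G2 at SD 20%.** n = 2 × 10.51 × (20/10)² = 84.1, so 85; the t-test gives 85.03, so 86. With 10% dropout, 85/0.9 = 94.4 and 86/0.9 = 95.6, so 95-96 randomised.

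**The case against.** Several points can be made for the plan.

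- The sentence is not false: 55 is sufficient for 90% power, with room to spare. This stands. The more serious fault is that 55 is not the enrolled size.
- The 41% pairs G2's 10% with G1's SD of 20%, and G2 gives no SD. With an SD near 10%, power for the same difference at 25 per group is 93-94%, which G1 already reports. This also stands: 41% is the low end of the plan's own range and must be read with its SD. The like-for-like contrast for 15% at SD 20% is 90% stated against 74%.
- The 15% in G1 is a detectable difference and the 10% in G2 a predicted one, and G2's back-reference may point to the 5-10% range in G1. That reading is possible. The two need not conflict, but the plan does not say which is the planning value.
- This is a pilot, LTS is secondary, its p-value is to be interpreted only if FVC is significant, and low power is conceded. All true, and it limits the harm. But the concession gives no figure at SD 20% and leaves the 90% statement in place.
- G4 plans a longitudinal model, not a t-test on change scores. Power under that model could differ somewhat. The plan gives no correlation between baseline and follow-up, so this cannot be computed, and the figures above are approximations. It does not reconcile 55 with 25.

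**Conclusion.** The concern holds. The stated size and power for LTS describe neither this trial nor the 90% size for the stated inputs. For 15% at SD 20%, power is about 74% with 25 per group and 68% with 22 completers, against 90% stated. For the 10% predicted in G2 at the same SD it is about 41% and 37%. The paragraph also changes sample size without notice, since its second power range belongs to 25 per group. These figures assume a two-sided 0.05 t-test on change scores, with the plan's 20% taken as the SD of change.

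The error should be corrected, but its consequences are small. Enrolment, procedures and analysis do not depend on 55, and the next trial's size would come from the LTS data observed in this one.

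**What to change.** In G1, replace the 55-per-group statement with the approximate power of the actual design. Suggested text:

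> With 25 randomised (about 22 evaluable) per group, an SD of LTS change of 20% and a two-sided 0.05 t-test on change scores, power is about 74% (68% at 22) for a 15% difference and about 41% (37% at 22) for the 10% difference predicted in G2. Power of 90% is reached only for differences of about 19% (20% at 22). Power under the planned longitudinal model may differ somewhat.

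In the sentence on an SD near 10%, say that the size meant is 25 per group and add the range for 22 completers (about 37-90%). State whether 15% or 10% is the planning difference for LTS, and make the reference in G2 match. If 55 was meant for the later trial, say so and give its assumptions, or replace it with 38-39 evaluable (43-44 randomised) per group for 15%, or 85-86 (95-96) for 10%. Keep the closing caveat about low power.

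The cost is a few sentences in G1 and one cross-reference to G2. Enrolment, procedures and analysis are unchanged; the stated LTS power becomes less favourable.
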